### Hematology:

Complete blood count (CBC) with total and differential white blood cell count (WBC)

### Serum chemistry:

Total bilirubin, Alk Phos, AST, ALT, serum creatinine, sodium, potassium, calcium, troponin I (troponin I mandatory at the Screening Visit, Visit 3, Visit 9 and in addition at any other visits only if clinically indicated)

### Pregnancy test:

A  $\beta$ -human chorionic gonadotropin (HCG) pregnancy test will be conducted for all WOCBP at screening, within 24 hours prior to each vaccination and at the individual last active trial phase visit. At Screening Visit, a serum  $\beta$ -HCG pregnancy test will be performed; all other pregnancy tests will be conducted as either urine or serum  $\beta$ -HCG tests.

The following parameters will only be evaluated during the screening period for assessment of inclusion / exclusion criteria:

HIV

Hepatitis B surface antigen

Antibodies against hepatitis C virus

Cholesterol (total Cholesterol, HDL, LDL)

## 8.2.9 Pregnancy

As per inclusion criteria, women of childbearing potential must have a negative serum pregnancy test at Screening Visit and a negative serum or urine pregnancy test within 24 hours prior to each vaccination. In addition, they must have used an acceptable method of contraception for 28 days prior to the first vaccination, must agree to use an acceptable method of contraception during the trial, and must avoid becoming pregnant for 28 days after the last vaccination. Nevertheless, IMP

exposed pregnancies cannot be excluded with certainty. Subjects who become pregnant prior to the first vaccination will be excluded from the trial and are regarded as screening failure. Subjects who become pregnant during the active trial period (up to and including one month [minimum 28 days] after receiving a dose of vaccine) must not receive additional doses of vaccine but may continue other trial procedures at the discretion of the investigator (Withdrawal from Further Trial Vaccination see [Section 4.2.5](#)). All IMP exposed pregnancies (i.e. up to 28 days after IMP administration) should be followed up until term or termination.

Subjects should be instructed to notify the investigator or designee if it is determined – also after completion of the trial - that they became pregnant either during the trial or within one month (minimum 28 days) after receiving the last vaccine dose.

## 8.3 Reporting

### 8.3.1 Reporting of Serious Adverse Events

All SAEs occurring throughout the entire course of the trial have to be reported to the CRO Drug Safety (DS) Department. The clinical trial site has to send by e-mail or fax the completed SAE form to the CRO DS Department within 24 hours of becoming aware of the SAE.

SAE reports should be faxed to the following number:

[figure not shown]
(b) (1) (A)

The investigator should not delay reporting because of missing information. Nonetheless, the report should be as complete as possible. This initial notification should include, as a minimum, sufficient information to permit identification of the following:

- the reporter (investigator's name and contact information)
- the subject
- involved trial medication
- AE(s)
- Seriousness criterion and/or criterion for AE
- date of onset

The CRO DS Department alerts BN Pharmacovigilance (PV) Department of all SAEs and provides the available information within 24 hours. BN is responsible for expedited as well as periodic reporting to the involved regulatory authorities (e.g. FDA, Paul-Ehrlich-Institut) according to applicable laws and guidelines. Regulatory authorities will be notified as soon as possible but no later than 7 days after first knowledge of fatal or life-threatening unexpected SAE with an at least possible relationship to the IMP (serious adverse drug reaction [SADR]) and no later than 15 days after knowledge of any other unexpected SADR. In addition BN will report the SAEs to the responsible Biomedical Advanced Research and Development Authority (BARDA) representative when applicable and forward them to the DSMB. All unanticipated problems involving risk to subjects or others and SAEs related to trial participation will be promptly reported to the HQ USAMRMC IRB by phone ((b) (1) (A)), by e-mail ((b) (1) (A)), or by facsimile ((b) (1) (A)), or sent to the U.S. Army Medical Research and Materiel Command, ATTN: ((b) (1) (A)). A complete written report will follow the initial notification. All other adverse events will be reported at Continuing Review. [Figure 2](#) outlines the reporting process and timelines for SAEs.

[figure not shown]
**Figure 2 Algorithm for Reporting of SAEs**

### 8.3.2 Reporting of Adverse Event of Special Interests

AESIs occurring throughout the entire course of the trial will be reported as outlined in [Figure 3](#).

**Figure 3** Algorithm for Reporting of AESIs

### **8.3.3 Reporting of Pregnancy**

If a subject becomes pregnant during the active trial period (up to and including one month [minimum 28 days] after receiving a dose of vaccine) this pregnancy must be reported to BN on a Pregnancy Report Form within 24 hours of the investigator's becoming aware of the event. If ACAM2000® is administered during pregnancy or if the vaccinee lives in the same household with or has close contact with a pregnant woman the vaccinee should be apprised of the potential hazard to the fetus. These cases will be reported to the OHU&E and/or HQ USAMRMC IRB as appropriate.

A reportable pregnancy should be followed to term, any premature terminations reported, and the health status of the mother and child including date of delivery and the child's gender and weight should be reported to BN as soon as possible after delivery.

Any event during pregnancy fulfilling the criteria for an SAE will be reported as SAE to BN PV. However, hospitalization for delivery is a prospectively planned hospitalization and is not considered a SAE per se.

### **8.3.4 Health Recordkeeping Requirements for Investigational New Drug Products**

In accordance with Army Regulation (AR) 40-562, all IND vaccines that are administered must be recorded in the individual's permanent health record or DoD approved electronic Immunization Tracking System. For vaccines, the documentation is the same as that required for other vaccines with an annotation "IND" with the vaccine name. This recordkeeping requirement is in addition to any recordkeeping requirements of the FDA-approved IND protocol.

## **9 Statistical Considerations**

### **9.1 Randomization Procedure**

Randomized treatment assignments for the subjects will be done after confirmation of subject's eligibility. The randomization will be performed in a 1:1 ratio using a validated Interactive Web Randomization (IWR) portal provided by a third party organization (Endpoint). Endpoint will store the randomization list in a secure environment. A fixed block size will be used for the randomization, but the block size will not be generally known by the clinical trial team.

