## **4 Trial Design**

### **4.1 Experimental Design**

This trial is a randomized, open-label Phase III non-inferiority trial to demonstrate efficacy for MVA-BN® compared to ACAM2000® in 18 to 42 year old healthy, vaccinia-naïve subjects.

#### Group 1

MVA-BN®, two standard doses s.c., 4 weeks apart followed by one dose of ACAM2000® via scarification 4 weeks after the second MVA-BN® vaccination.

#### Group 2

ACAM2000®, one dose via scarification, in accordance with US military smallpox vaccine program.

Subjects in Group 1 will participate in eleven physical trial visits, nine blood draws and one remote follow-up visit. Subjects in Group 2 will participate in seven physical trial visits, seven blood draws and one remote follow-up visit. For the schedule of the trial visits and the description of trial procedures, please refer to the trial procedure schedule and the following protocol sections.

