### Visit 1 (Day 0)

Tasks to be performed prior to randomization and vaccination:

- Re-check inclusion/exclusion criteria
- Check of safety laboratory results obtained at Screening Visit
- Targeted physical examination, including auscultation of heart and lungs, see [Section 8.2.3](#) for more details
- Evaluation of vital signs
- Recording of baseline signs and symptoms
- Questions on cardiac signs and symptoms
- Review of prior/concomitant medications
- Assessment of axillary and supraclavicular lymphadenopathy, see [Section 8.2.3](#) for more details
- Examination of the possible deltoid vaccination sites
- Counseling on avoidance of contact spread (specifically after ACAM2000® vaccination), HIV infection and pregnancy
- Urine or serum pregnancy test (5 ml, if applicable)
- Blood draw (serum collection) for antibody analysis (16 ml)

Blood draws and all other tasks mentioned above must always be performed prior to vaccination. If the subject is still eligible for participation in this trial, the subject will be randomized. The following tasks will be performed after randomization:

- Vaccination: Group 1: administration of one (1) dose of MVA-BN®  
Group 2: administration of one (1) dose of ACAM2000®
- Subject observation by clinical trial site staff for at least 30 minutes after vaccination

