## 7 Assessment of Immunogenicity and Efficacy

### 7.1 Humoral Immune Response

Analysis of humoral immune response is planned to occur at Visit 1 (baseline measurement) through Visit 4 for both groups and additionally for the Group 1 subjects at Visit 6, Visit 7 and at Visit 10 and for Group 2 subjects at Visit 5 and 6. Baseline (i.e. Visit 1 [Week 0]), Visit 4 (Week 4) and Visit 7 (week 8) blood samples will be drawn prior to any scheduled vaccination.

The immune response measured at the Peak Visits by validated vaccinia-specific PRNT and vaccinia-specific ELISA will be used as the relevant immunologic response for the assessment of non-inferiority.

Antibody responses to MVA-BN® and ACAM2000® will be measured using a vaccinia-specific PRNT and a vaccinia-specific ELISA which were established and validated at BN. Endpoint GMT titers will be done on all subjects, independent from their baseline immune status. The tests will be performed at BN, Martinsried, Germany. All immunological clinical analysis personnel will be blinded to subject randomization details.

The methods for collection, storage and handling of lab specimens for the immune analysis are specified in a separate manual which will be provided to the investigators before enrollment. Additionally, training will be provided on the procedures during the investigator meeting and/or at the initiation visit. The protocols for the analytical tests performed are detailed in the BN SOPs listed below in the assay sections. Copies of the SOPs (from BN and the CRO), effective at the time of trial conduct will be filed in the Trial Master File.

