3.1 Randomization Procedure

Target enrollment in the trial is 440 subjects to be vaccinated (220 subjects in Group 1 and 220 subjects in Group 2). Randomized treatment assignments for the subjects will be done after confirmation of subject's eligibility. Subjects will be allocated randomly into either Group 1 or Group 2 across the one clinical trial site in a 1:1 ratio. There will not be any stratification factors used in the randomization.

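### A fixed block size in an open-label, single-site, unstratified trial lets staff who track assignments infer the block length and know end-of-block assignments in advance

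*Protocol*

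**What the plan says.** Protocol 9.1 assigns subjects 1:1 through a third party's web system, which holds the list securely, once eligibility has been confirmed. On the block structure it says only: "A fixed block size will be used for the randomization, but the block size will not be generally known by the clinical trial team". SAP 3.1 allocates subjects "across the one clinical trial site in a 1:1 ratio. There will not be any stratification factors used in the randomization".

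Protocol 4.1 gives the design: "This trial is a randomized, open-label Phase III non-inferiority trial". Under Protocol 4.2.2, Group 1 receives a subcutaneous injection on Day 0, while Group 2 is scarified and leaves with a bandage and care kit. Each assignment is therefore plain to the staff as soon as it is carried out.

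At Visit 1 the entry criteria are checked again, and then "If the subject is still eligible for participation in this trial, the subject will be randomized". Outcome assessment has its own protection. In Protocol 7.1, "All immunological clinical analysis personnel will be blinded to subject randomization details", and Protocol 7.5 sets up a blinded committee to review the takes.

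Neither document states the block length, varies it, or describes any further measure against prediction.

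**The concern.** With one site and no strata there is a single sequence of blocks, and with open-label vaccines the site sees all of it. When the block length is fixed, the two groups return to equal numbers at regular intervals. A person who keeps a tally can work out the interval, so withholding the length is weak protection. Once the length is known, any assignment made after one group's places in the block are used up is known before the subject is randomised.

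Foreknowledge matters only if there is room to act on it, and there is some:

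- Inclusion criterion 3 and exclusion criterion 5 (Protocol 5.2 and 5.3) call for judgement.
- The screening window of up to 70 days (Protocol 4.2.1) leaves freedom over when and in what order subjects come for Visit 1.
- The groups carry different burdens: eleven physical visits against seven (Protocol 4.1). The Per Protocol Set requires completion to Visit 10 in Group 1 but only to Visit 4 in Group 2 (SAP 3.7.2). A subject thought unlikely to attend could be steered away from Group 1.

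What is at stake is the comparability of the groups at entry, on which both unadjusted co-primary comparisons rest.

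**Working it through.** **Plan figures.** The documents give no figure for block length or predictability, so there is none to reproduce on this point. The only plan figure used is the total of 440 (SAP 1.1). The sample size is not in dispute: 2 × (1.960 + 1.282)² × 0.866² / 0.301² = 174 per group, and a noncentral-t check gives 90.0% power at the stated 175.

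**Step 1: share certain in advance, block length known.** For a 1:1 block of 2m, the expected number of assignments left after one group's places run out is 2m/(m+1), so the share is 1/(m+1). For a block of 4, the fourth assignment is always certain and the third is certain with probability 1/3. That gives 1.333 per block, and 1.333/4 = 33%.

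**Step 2: best guess.** An observer who always names the group with more places left scores, in a block of 4, 1/2 + 2/3 + 2/3 + 1 = 2.833 of 4, or 71%. Chance is 50%. Other lengths were enumerated in the same way. The lengths are assumptions.

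| Assumed length | Certain in advance | Best guess correct |
|---|---|---|
| 4 | 33% | 71% |
| 6 | 25% | 68% |
| 8 | 20% | 67% |
| 10 | 17% | 65% |
| 20 | 9% | 62% |

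**Step 3: how soon the length could be inferred.** This was simulated with 1,000 runs per length, for an observer who records every assignment and gives equal prior weight to lengths 2, 4, 6, 8, 10 and 12. The observer is taken to know the length at 95% posterior probability.

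| True length | Median subjects seen | 90th percentile |
|---|---|---|
| 2 | 32 | 32 |
| 4 | 42 | 60 |
| 6 | 42 | 63 |
| 8 | 36 | 78 |
| 10 | 24 | 48 |

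The largest median is 42/440 = 10% of enrolment, and the largest 90th percentile is 78/440 = 18%. Adding further candidate lengths could only lengthen these times.

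**Step 4: numbers of subjects.** The shares apply to assignments made after the length is known. At the median times:

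- length 4: (440 − 42)/3 = 133
- length 6: (440 − 42)/4 = 100
- length 8: (440 − 36)/5 = 81
- length 10: (440 − 24)/6 = 69

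**Step 5: randomly varying sizes.** An observer who knows the set of sizes but not their order was simulated over 440 subjects.

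| Sizes mixed | Certain in advance | Best guess correct |
|---|---|---|
| 4, 6 | about 5% (24 of 440) | 69% |
| 4, 6, 8 | about 2% (10 of 440) | 68% |
| 6, 8, 10 | about 2% (7 of 440) | 66% |

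Mixing sizes removes most of the certainty but hardly changes the best-guess rate.

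**The case against.** The strongest case against is that this is a deliberate, openly stated choice with no internal contradiction, and that several safeguards limit any harm. The list is held by a third party, the length is withheld, and randomisation follows the eligibility check. Many entry criteria are objective laboratory, ECG or history items. The Visit 1 serum is drawn just before randomisation and is assayed by blinded laboratory staff, so the site has no titer to select on. Lesion areas are confirmed by a blinded committee. SAP 3.10.4 compares baseline characteristics between groups, and SAP 1.4.1 repeats the co-primary analyses on the Full Analysis Set. The undisclosed length may also be long, and at 20 only 9% of assignments are certain.

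Much of this stands as a limit on the size of the concern, but it does not remove it. Blinded outcome assessment protects measurement, not who enters each group. Baseline tests can reveal some imbalance in measured characteristics, but not selection on something unmeasured, such as expected attendance. Checking eligibility before randomisation does not help if the next assignment is already known and the check involves judgement.

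A reader might also infer that staff may freely defer a subject at Visit 1. The text does not support that. Deferral in Protocol 4.2.2 concerns vaccination, is tied to acute illness and must stay within the visit window.

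**Conclusion.** The concern holds as a weakness in allocation concealment that is cheap to remove. Staff who track assignments could learn the block length within roughly the first tenth of enrolment. They would then know 33%, 25%, 20% or 17% of the remaining assignments for lengths of 4, 6, 8 or 10. For a length of 20 the share is 9%, but the time to learn that length was not assessed. These figures assume an observer who sees and records every assignment. The block lengths are assumptions, because the documents give none.

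Three stronger readings are tempting and are not supported:

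- A reader might infer that upcoming assignments in general can be predicted. Only the end of a block is certain; the rest can be guessed at better than chance.
- A reader might multiply 20% to 33% by 440 and report 88 to 147 known assignments. That assumes a length between 4 and 8, and knowledge of it from the first subject.
- A reader might conclude that both co-primary comparisons are biased. The documents show an opportunity, not its use, and they give no link from selection at entry to PRNT titer or lesion area. The effect could be nil and cannot be quantified.

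**What to change.** Change the block-size sentence in Protocol 9.1 to say that the vendor generates the list, or its unused remainder if enrolment has begun, in permuted blocks of randomly varying size (for example 4, 6 and 8). It should also say that the sizes and their order are withheld from site and sponsor staff. The gain is limited to assignments not yet made. Those certain in advance fall to about 2%, while better-than-chance guessing remains at about 68%, against 67% to 71% with a fixed block of 4 to 8.

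The cost is a vendor list update and re-check of the web system, IRB approval of the amended sentence before use (Protocol 13.1), and a possible imbalance of a few subjects at the end. An unfinished final block of 8 leaves a difference of at most 4. The sample size and the analyses do not change.

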### **9.2 Co-Primary Trial Hypotheses**

#### **9.2.1 Immunogenicity Hypothesis**

The immunogenicity co-primary endpoint is to assess non-inferiority of MVA-BN® compared to ACAM2000® in terms of antibody response at the Peak Visit, i.e. 28 days after an ACAM2000®

vaccination and 42 days after the first MVA-BN® vaccination measured by validated vaccinia-specific PRNT.

Suppose  $m_1$  is the PRNT  $\log_{10}$  titer mean in Group 1 (MVA-BN® followed by ACAM2000®) and  $m_2$  is the PRNT  $\log_{10}$  titer mean in Group 2 (ACAM2000® only). The test of non-inferiority will be applied for the following hypothesis:

$$H_0: m_1 - m_2 \leq -\Delta \text{ versus } H_1: m_1 - m_2 > -\Delta \text{ where}$$

$\Delta$  is the non-inferiority margin. For the PRNT the non-inferiority margin will be 0.301 on the  $\log_{10}$  scale (which is equivalent to a doubling on the original titer scale for the GMT). This is the same  $\Delta$  as was used for the assessment of non-inferiority of ACAM2000® to Dryvax® ([ACAM2000 VRBPAC Briefing Document, April 2007](#)).

The above hypotheses will be tested for the PRNT using a t-test on the difference of the two means based on the assumption that the  $\log_{10}$  titer values have a normal distribution (which has been the case in all previous MVA-BN® studies). Specifically, a one-sided 97.5% confidence interval for the difference of the  $\log_{10}$  titer means (based on the assumption of a common standard deviation [SD]) will be calculated. If the lower limit of this confidence interval is greater than  $-\Delta$ , then the null hypothesis will be rejected for the respective assay and non-inferiority of MVA-BN® to ACAM2000® will have been demonstrated.

### 9.2.2 Efficacy Hypothesis

The efficacy co-primary hypothesis of the trial is to assess if the median of the MLA following ACAM2000® vaccination is significantly reduced for subjects in Group 1 who received prior MVA-BN® vaccinations compared to those in Group 2 who received no prior MVA-BN® vaccinations. Specifically the ratio of each median plus one will be tested:

$$H_0: 1 - \frac{M_1}{M_2} \leq \lambda \quad \text{versus} \quad H_1: 1 - \frac{M_1}{M_2} > \lambda$$

i.e. the null hypothesis ( $H_0$ ) is that 1 minus the ratio in median MLA in Group 1 ( $M_1$ ) over the median MLA in Group 2 ( $M_2$ ) is less than or equal to a predefined constant  $\lambda$ , which is tested against the one-sided alternative hypothesis ( $H_1$ ) that the ratio  $> \lambda$ . This test will be performed by using the 95% asymptotic Hodges-Lehmann confidence interval ([Lehmann, 1975](#)) on the  $\log_{10}$  MLA values and the confidence limits will be anti-logged back on to the original scale (see Statistical Analysis Plan for further details). Specifically, only the anti-log of the upper 95% Hodges-Lehmann confidence interval of the  $\log_{10}$  MLA values between groups is used, with a one-sided significance level of 2.5%, and this needs to be below  $1-\lambda$  for the null hypothesis to be rejected, and thus the co-primary endpoint will be met. However, for completeness the upper and lower confidence limits along with the point estimate of the Hodges-Lehmann shift estimator (which can be slightly different from the ratio of medians) will be reported. Note that a positive

offset of 1 will be added to any zero MLA values in order to avoid problems with taking logarithms of zero.

The clinical justification of the choice of  $\lambda=40\%$  is that this is the reduction that has been seen in vaccinia-experienced subjects compared to vaccinia-naïve subjects who were (re-)vaccinated with a first generation smallpox vaccine (Talbot, 2006) and is discussed further in the attached Statistical Analysis Plan.

If one or both of the day 6-8 or day 13-15 photographs are missing then the photograph will be recorded as missing and the assessment of attenuation will not be made.

### **9.3 Endpoints**

#### **9.3.1 Co-Primary Endpoints**

- PRNT GMT at the Peak Visits
- MLA in mm^2 after scarification with ACAM2000®

#### **9.3.2 Secondary Endpoints**

##### **Immunogenicity**

GMT at the Peak Visits and individual peak measured by vaccinia-specific ELISA.

GMTs at the individual peak measured by vaccinia-specific PRNT.

GMTs at all antibody blood sample time points measured by vaccinia-specific PRNT and vaccinia-specific ELISA.

PRNT seroconversion rates at Peak Visits defined as the percentage of initially seronegative subjects with appearance of antibody titers equal or greater than the ACV in a vaccinia-specific PRNT.

ELISA seroconversion rates at Peak Visits defined as the percentage of initially seronegative subjects with appearance of antibody titers equal or greater than the ACV in a vaccinia-specific ELISA.

